## 2. GLOSSARY OF ABBREVIATIONS AND DEFINITION OF TERMS

|        |   |
|--------|---|
| AZA    | azacitidine                                     |
| CI     | confidence interval                             |
| CR     | complete remission                              |
| eCRF   | electronic case report form                     |
| DCR    | duration of complete remission                  |
| DOR    | duration of response                            |
| ECOG   | Eastern Cooperative Oncology Group              |
| EDC    | electronic data capture                         |
| EEAS   | Effectiveness Evaluable Analysis Set            |
| EHR    | electronic health record                        |
| FAS    | Full Analysis Set                               |
| Gilead | Gilead Sciences                                 |
| GPP    | Good Pharmacoepidemiology Practices             |
| HI     | hematologic improvement                         |
| iKM    | iKnowMed  |
| IRB    | institutional review board                      |
| IPSS-R | Revised International Prognostic Scoring System |
| IWG    | International Working Group                     |
| LADMF  | Limited Access Death Master File                |
| mCR    | marrow complete remission                       |
| MDS    | myelodysplastic syndrome                        |
| OR     | objective response                              |
| ORR    | objective response rate                         |
| OS     | overall survival                                |
| PFS    | progression-free survival                       |
| PR     | partial remission                               |
| Q1     | first quartile                                  |
| Q3     | third quartile                                  |
| rw-CR  | real-world complete remission                   |
| RWD    | real-world data                                 |
| rw-DCR | real-world duration of complete remission       |
| rw-DOR | real-world duration of response                 |
| rw-OR  | real-world objective response                   |
| rw-ORR | real-world objective response rate              |
| rw-PR  | real-world partial response                     |
| SSN    | social security number                          |

|         |   |
|---------|---|
| TTNT    | time to next treatment                  |
| USON    | The United States Oncology Network      |
| US, USA | United States, United States of America |

### 3. PROTOCOL SYNOPSIS

**Gilead Sciences**  
**[name]**  
**[name]**

---

**Study Title:** A retrospective observational cohort study to evaluate the effectiveness of azacitidine monotherapy in treatment-naive patients with intermediate, high, and very high-risk myelodysplastic syndrome (MDS)

---

**Rationale and Background:** Magrolimab, an investigational CD47 targeting monoclonal antibody is being evaluated in combination with azacitidine (AZA) in patients with treatment-naive intermediate, high, and very high-risk MDS by the Revised International Prognostic Scoring System (IPSS-R), also known as higher-risk MDS (study 5F9005). In order to evaluate the contribution of magrolimab to the outcomes seen with the combination treatment, this retrospective study will be conducted to investigate the effectiveness of AZA monotherapy in the real-world setting.

This retrospective cohort study will include patients who have initiated treatment with AZA in the past as identified from The United States Oncology Network (USON) database. This study will utilize USON's iKnowMed (iKM) electronic health record (EHR) and supplemental vitality status from the Limited Access Death Master File (LADMF). All necessary data will be abstracted by structured data query supplemented by chart review of unstructured data elements.

---

**Research Question and Objectives:** The primary objective of this study is as follows:

- To evaluate the effectiveness of AZA monotherapy, as assessed by complete remission (CR) rates defined by the International Working Group (IWG) 2006 MDS criteria in patients with intermediate-, high-, and very high-risk MDS

The secondary objectives of this study are as follows:

- To evaluate additional measures of effectiveness including the real-world CR (rw-CR) rate, objective response rate (ORR) defined by IWG 2006 MDS criteria, real-world objective response rate (rw-ORR), duration of complete remission (DCR) and its real-world equivalent, and the duration of response (DOR) and its real-world equivalent of AZA in this study population
- To evaluate progression-free survival (PFS), time to next treatment (TTNT), and overall survival (OS) of AZA in this study population

The exploratory objectives of this study are to evaluate the following in this study population:

[REDACTED]

---

**Study Design:**

This retrospective cohort study will include patients with intermediate-, high-, and very high-risk MDS who have been treated with AZA in routine clinical practice in the US who will be identified from the USON EHR database. This study will utilize USON's iKM EHR and supplemental vitality status from the LADMF. Data will be abstracted by structured data query and by chart review of unstructured data into an electronic case report form (eCRF).

All intermediate, high, and very high-risk patients with MDS who were initiated on AZA monotherapy will be eligible to be included in the study. The study will be conducted in 2 stages. In Stage 1, all patients meeting the inclusion/exclusion criteria based on structured data from the iKM EHR database and initiated AZA as first-line treatment between 01 January 2014 through 01 January 2020 will be identified. About twenty patients will be randomly selected among the patients for a pilot chart review. The purpose of the pilot is to assess data quality (fit-for-purpose assessment) including the quantification of missing data; no data analyses will be performed. In Stage 2, chart review will be conducted in all patients who initiated AZA from 01 January 2014 to 01 January 2020. To allow for a minimum of 1 year of follow-up after the initiation of AZA, the last patient initiation should be on or before 01 January 2020.

Patient demographics and baseline characteristics, including IPSS-R risk category, clinical characteristics, all supportive treatment before initiating AZA, concomitant medications, progression data, next line of therapy for the treatment of MDS, and survival status, will be collected from the date of initiation of AZA until 01 January 2021 or death, whichever is the earlier.

Data extracted from the EHR through an eCRF will be collected into an electronic data capture (EDC) system. Data from structured query will be compiled together with EDC data for analysis.

---

**Population:**

Adult ( $\geq 18$  years) patients in the US with documented histological diagnosis of MDS as per medical record documentation in the EHR and who are classified as intermediate, high, or very high risk according to IPSS-R treated with AZA monotherapy as first-line treatment in standard clinical practice in line with AZA prescribing information.

---

---

|                       |  |
|-----------------------|--|
| Variables:     | This is an observational retrospective cohort study. Only data available from routine medical practice will be collected within the study. Variables include patient demographics, clinical and disease characteristics, AZA treatment-related variables, laboratory assessments, and treatment response assessments.  |
| Data Sources:  | The primary data source will be the EHR. Eligible patients will be identified from the iKM EHR database. Supplemental vitality status will be obtained from the LADMF.   |
| Study Size:    | A sample size of approximately 400 patients will provide adequate precision to estimate CR rates. The width of a 2-sided 95% exact confidence interval (CI) of CR rate is $\leq 10\%$ for an observed CR rate in the range of 5% to 25% if sample size is $> 300$ .  |
| Data Analysis: | 
Continuous variables will be summarized by mean, standard deviation, median, 25% quantile, 75% quantile, minimum and maximum. Categorical variables will be summarized by number and percentage of patients in each categorical definition including 95% CIs. Time-to-event endpoints will be described using the Kaplan-Meier method. The Full Analysis Set (FAS) includes all enrolled patients who took at least 1 dose of AZA. The Effectiveness Evaluable Analysis Set (EEAS) includes all FAS patients who had at least 1 response assessment or died after the index date.
 
The effectiveness analyses (except DCR, real-world duration of complete remission [rw-DCR], DOR, and real-world duration of response [rw-DOR]) will be performed on the FAS. DCR and rw-DCR will be evaluated using FAS patients who achieve a CR and rw-CR, respectively. DOR and rw-DOR will be evaluated using FAS patients who achieve an objective response (OR) and real-world objective response (rw-OR), respectively. Sensitivity analyses will be performed for the primary and secondary endpoints (except DCR, rw-DCR, DOR, and rw-DOR) using EEAS.
 
Details of analytical comparison with magrolimab and AZA combination therapy trial (5F9005) data will be included in the statistical analysis plan.
 |
| Milestones:    | Start of data collection: first quartile (Q1) 2021
Interim and Progress report: Not Applicable
End of Data collection: first quartile (Q1) 2021
Final Study report: third quartile (Q3) 2021  |

---

This study will be conducted in accordance with the guidelines of Good Pharmacoepidemiology Practices (GPP) including archiving of essential documents.

#### 4. AMENDMENTS AND UPDATES

**Table 4-1. Protocol Amendments and Updates**

| Amendment or Update Number | Date | Section of Study Protocol | Amendment or Update | Reason |
|-----------------------------------|-------------|----------------------------------|----------------------------|---------------|
| None                              | NA          | NA                               | NA                         | NA            |

NA not applicable

#### **Protocol Modifications**

Protocol modifications may only be made by Gilead.

## 5. MILESTONES

**Table 5-1. Protocol Milestones**

| Milestone              | Planned Date |
|-------------------------------|---------------------|
| Start of data collection      | Q1 2021             |
| End of data collection        | Q1 2021             |
| Final report of study results | Q3 2021             |

Q1 first quartile; Q3 third quartile

## 6. RATIONALE AND BACKGROUND

### 6.1. Rationale for the Current Study

Myelodysplastic syndrome (MDS) is a pre-malignant condition characterized by peripheral cytopenias due to production of dysfunctional, dysplastic bone marrow (BM) cells. Low- and very low-risk patients, as defined by the Revised International Prognostic Scoring System (IPSS-R) {[Greenberg 2012](#)}, are often treated with erythroid and myeloid growth factor support and carry a low risk of leukemic progression.

In contrast to lower risk MDS, intermediate-, high-, and very high-risk MDS, collectively known as ‘higher risk’ MDS, carries a high risk of leukemic progression. Azacitidine (AZA) is the standard of care for these patients in the frontline setting. However, complete remission (CR) rates are low with AZA therapy, and overall survival (OS) is only approximately 13 months {[Silverman 2002](#)}. Thus, novel therapies that replace or augment the effectiveness of AZA are needed to extend survival for patients with MDS.

Magrolimab has been investigated in a Phase 1b single-arm study (Study 5F9005) in multiple subtypes of acute myeloid leukemia, very low-/low-risk MDS, and intermediate-/high-/very high-risk MDS, both as monotherapy and in combination with AZA. Specifically, magrolimab is being evaluated in combination with AZA in frontline MDS in patients with intermediate-, high-, and very high-risk MDS by IPSS-R in a potentially registrational cohort. In order to evaluate the contribution of magrolimab to the outcomes seen with the combination treatment for this specific population, this retrospective study will be conducted to investigate the effectiveness of AZA monotherapy in the real-world setting. A separate analysis plan will be developed for comparison with trial data.

This protocol describes the objectives and methodology used to obtain and analyze real-world data (RWD), including patient level data, derived from electronic health records (EHR).

## 7. RESEARCH QUESTIONS AND OBJECTIVES

The primary objective of this study is as follows:

- To evaluate the effectiveness of AZA monotherapy as assessed by CR rate defined by the International Working Group (IWG) 2006 MDS criteria in patients with intermediate-, high-, and very high-risk MDS

The secondary objectives of this study are as follows:

- To evaluate additional measures of effectiveness including the real-world CR (rw-CR) rate, objective response rate (ORR) defined by IWG 2006 MDS criteria, real-world objective response rate (rw-ORR), duration of complete remission (DCR) and its real-world - equivalent, and the duration of response (DOR) and its real-world equivalent of AZA in this study population
- To evaluate progression-free survival (PFS), time to next treatment (TTNT), and overall survival (OS) of AZA in this study population

The exploratory objectives of this study are to evaluate the following in this study population:

- [REDACTED]
- [REDACTED]
- [REDACTED]
- [REDACTED]

## 8. RESEARCH METHODS

### 8.1. Study Design

This is an observational cohort study utilizing a retrospective chart review of patients with higher-risk MDS treated in a real-world setting with AZA according to routine clinical practice in the United States.

Study data will be analyzed from EHR at the US Oncology Network (USON) and supplemental vitality status from the Limited Access Death Master File (LADMF). Structured data will be collected via programmatic queries of iKnowMed (iKM). To supplement these structured data elements, a targeted chart review will be performed to capture unstructured data on all patients.

#### 8.1.1. Primary Endpoint

**Complete Remission Rate** is defined as the proportion of patients who achieve a CR as documented within their EHRs, with confirmation of corresponding BM and peripheral blood parameters as defined per IWG 2006 MDS response criteria {Cheson 2006}, during the treatment period with AZA or prior to the initiation of next MDS treatment.

Definitions of responses categories are shown in [Table 8-1](#) below.

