### 8.1.2. Secondary Endpoints

**Real -World Complete Remission (rw-CR) Rate** is defined as the proportion of patients who achieve a CR as documented within their EHRs with or without confirmation of corresponding BM and peripheral blood parameters as defined per IWG 2006 MDS response criteria, during the treatment period with AZA or prior to the initiation of next MDS treatment.

**Objective Response Rate (ORR)** is defined as the proportion of patients who achieve a CR, or PR as documented within their EHRs with confirmation of corresponding BM and peripheral blood parameters as defined per IWG 2006 MDS response criteria, or achieve an mCR or HI, during the treatment period with AZA or prior to the initiation of next MDS treatment.

**Real -World Objective Response Rate (rw-ORR)** is defined as the proportion of patients who achieve a CR, or PR, as documented within their EHRs with or without confirmation of corresponding BM and peripheral blood parameters as defined per IWG 2006 MDS response criteria, or achieve an mCR or HI, during the treatment period with AZA or prior to the initiation of next MDS treatment.

**Duration of CR (DCR)** is defined as the interval from the first EHR documentation of a CR with confirmation of corresponding BM and peripheral blood parameters as defined per IWG 2006 MDS response criteria to the earlier of the first documentation of relapse, disease progression, or death from any cause.

**rw-DCR** is defined as the interval from the first EHR documentation of a CR with or without confirmation of corresponding BM and peripheral blood parameters as defined per IWG 2006 MDS response criteria to the earlier of the first documentation of relapse, disease progression, or death from any cause.

**Duration of Response (DOR)** is defined as the interval from when the criteria are first met for OR to the earlier of the first documentation of relapse, disease progression, or death from any cause.

**rw-DOR** is defined as the interval from when the criteria for rw-OR are first met to the earlier of the first documentation of relapse, disease progression, or death from any cause.

**Progression -Free Survival** is defined as the interval from the date of initiation of AZA to the earlier date of the first documentation of relapse, disease progression or death from any cause.

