**Time to the next treatment** is defined as the interval from the date of initiation of treatment with AZA to the earlier date of the initiation of next anti-leukemic treatment of MDS (excluding palliative care or palliative radiation) or death from any cause.

**Overall Survival** is defined as the interval from the date of initiation of AZA to death from any cause.

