**Table 8-3. Eligibility Criteria**

|   | Stage 1
Criteria
applied
during
structured
data
extraction | Stage 1
Criteria to
confirm during
pilot chart
review
(Approximately
20 patients) | Stage 2
Criteria to
confirm
during full
chart review
(full sample) |
|---|---|--|---|
| Inclusion Criteria   |   |  |   |
| Patients must meet all the following inclusion criteria to be eligible:   |   |  |   |
| 1) Male or female $\geq 18$ years of age  | X   |  |   |
| 2) Documented histological diagnosis of MDS defined as per medical record documentation in the EHR  | X   | X  | X   |
| 3) Documented IPSS-R MDS risk category of intermediate, high, or very high risk   | X   | X  | X   |
| 4) Initiation of AZA monotherapy during the Study Index Period  | X   | X  | X   |
| 5) Received at least a single dose of treatment with AZA in line with US Prescribing information; the following dosing regimens are permitted:
a) AZA 75 mg/m  Days 1-7 of a monthly cycle
b) AZA 75 mg/m  Days 1-5, 8-9 of a monthly cycle (5 days on, 2 days off on the weekend, 2 days on)
c) AZA 75 mg/m  Days 1-5 of a monthly cycle  | X   | X  | X   |
| 6) Patients should not have received any anti-leukemic therapies for the treatment of MDS prior to the initiation of AZA. (Prior and concurrent therapy with hydroxyurea, oral etoposide, erythroid and/or myeloid growth factors, or any symptomatic treatment is allowed. Patients with MDS who received prior anti-cancer therapy from prior malignancies are permitted.)  | X   |  | X   |
| 7) Patients must have at least 1 posttreatment encounter in the EHR.  | X   |  |   |
| 8) WBC count $\leq 20 \times 10^3/\mu\text{L}$ at the time of AZA initiation (use of hydroxyurea to reduce WBC prior to AZA initiation, as documented within the EHR is acceptable).  | X   |  |   |
| 9) Adequate hepatic and renal function at the time of AZA initiation (within 30 days of index) as evidenced by the following documentation in the EHR:
a) AST and ALT $\leq 5 \times$ upper limit of normal (ULN)
b) Bilirubin $\leq 1.5 \times$ ULN, or $3.0 \times$ ULN and primarily unconjugated if patient has a documented history of Gilbert's syndrome or genetic equivalent
c) Serum creatinine $\leq 1.5 \times$ ULN or calculated glomerular filtration rate (GFR) $\geq 40$ mL/min/1.73 m  | X   |  |   |

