|  | Stage 1
Criteria
applied
during
structured
data
extraction | Stage 1
Criteria to
confirm during
pilot chart
review
(Approximately
20 patients) | Stage 2
Criteria to
confirm
during full
chart review
(full sample) |
|--|---|--|---|
| Exclusion Criteria  |   |  |   |
| 1) Any prior anti-leukemic therapy including chemotherapy (excluding hydroxyurea or oral etoposide), targeted therapies, immunotherapy or radiotherapy   | X   | X  | X   |
| 2) Prior treatment with hypomethylating agents and/or low dose cytarabine. Prior treatment with lenalidomide or similar agents is permitted if treatment is utilized for symptomatic support (ie, anemia, RBC transfusion dependence). | X   | X  | X   |
| 3) Patients participated in an interventional clinical trial during study observation period.  | X   | X  | X   |
| 4) Previous hematopoietic stem cell transplant within 6 months prior to initiation of AZA, active GVHD, or requiring transplant-related immunosuppression.   | X   | X  | X   |
| 5) Patients who have had transformation of MDS into AML prior to initiation of AZA   | X   | X  | X   |
| 6) Known inherited or acquired bleeding disorders  |   |  | X   |
| 7) EHR documentation of clinical suspicion/ radiological evidence of active CNS involvement by leukemia  |   |  | X   |
| 8) Acute promyelocytic leukemia  | X   |  | X   |
| 9) Second malignancy, except treated basal cell or localized squamous skin carcinomas, localized prostate cancer, or other malignancies for which patients are not on active anti-cancer therapy as defined in Exclusion Criterion 1   | X   |  | X   |
| 10) Patients who initiated AZA treatment outside the approved label (except as described under the Inclusion Criterion 5) for example, in combination with other agents for the treatment of MDS                                       |   |  | X   |

AML acute myeloid leukemia; ALT alanine aminotransferase; AST aspartate aminotransferase; AZA azacitidine; CNS central nervous system; ECOG Eastern Cooperative Oncology Group; EHR electronic health record; GVHD graft versus host disease; IPSS R Revised International Prognostic Scoring System; MDS myelodysplastic syndrome; RBC red blood cell; ULN upper limit of normal; US United States; WBC white blood cell

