| Dose Changes h   | 2     | Structured + Unstructured | X   | X            | X       | X         |                       |
| Dose Interruptions i   | 2     | Structured + Unstructured | X   | X            | X       | X         |                       |
| Discontinuation h  | 1&2   | Structured + Unstructured | X   | X            | X       | X         |                       |
| Reason for Treatment Discontinuation  | 1&2   | Unstructured              |   |              |         | X         | X                     |
| Data Related to Effectiveness  |       |                           |   |              |         |           |                       |
| Date of Response Assessment (From Progress Notes and/or Attachment for the Bone Marrow Report)                                | 1&2   | Unstructured              | X   | X            | X       | X         |                       |
| Response Category j (From Progress Notes and/or Attachment for the Bone Marrow Report)                             | 1&2   | Unstructured              | X   | X            | X       | X         |                       |
| IWG 2006 Response Assessment, Where Available k (From Progress Notes and/or Attachment for the Bone Marrow Report) | 1&2   | Unstructured              | X   | X            | X       | X         | X                     |
| If Progression, Date of Progression   | 1&2   | Unstructured              |   | X            | X       | X         | X                     |

| Data to be Provided if Available or Applicable                         | Stage | Source                            | Baseline (At AZA Initiation or Earlier as Applicable) | Study Period |         |           | Post-treatment Period |
|--|-------|-----------------------------------|---|--------------|---------|-----------|-----------------------|
|  |       |                                   |   | Visit 1      | Visit 2 | Visit (n) | Post-treatment        |
| Last USON Visit Date   | 2     | Structured + unstructured         |   | X            | X       | X         | X                     |
| Death Date   | 2     | Structured + LADMF + unstructured |   | X            | X       | X         | X                     |
| MDS Treatment After Discontinuation of AZA, if Applicable l | 1&2   | Structured + Unstructured         |   | X            | X       | X         | X                     |

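### Read literally, the response window credits azacitidine monotherapy with a response first reached after another anti-leukemic agent is added to continuing azacitidine

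*Protocol*

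**What the plan says.** The primary objective (Protocol Section 7) is "To evaluate the effectiveness of AZA monotherapy as assessed by CR rate defined by the International Working Group (IWG) 2006 MDS criteria". Section 6.1 gives the purpose: "In order to evaluate the contribution of magrolimab to the outcomes seen with the combination treatment for this specific population".

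Section 8.1.1 counts a CR if it is reached "during the treatment period with AZA or prior to the initiation of next MDS treatment". Section 8.1.2 uses the same window for rw-CR, ORR and rw-ORR; for the two objective response rates it ends "or achieve an mCR or HI, during the treatment period with AZA or prior to the initiation of next MDS treatment". TTNT, in the same section, runs from azacitidine initiation "to the earlier date of the initiation of next anti-leukemic treatment of MDS", or to death.

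In Table 8-3, Inclusion Criterion 4 requires "Initiation of AZA monotherapy during the Study Index Period", and Exclusion Criterion 10 removes "Patients who initiated AZA treatment outside the approved label", with combination use as its example. In Table 8-4 the row for later therapy is labelled "MDS Treatment After Discontinuation of AZA, if Applicable".

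**The concern.** The study is meant to measure what azacitidine achieves alone. The window has two limbs joined by *or*, with nothing to say that the earlier one governs. A patient who has a second anti-leukemic agent added and stays on azacitidine is still in the azacitidine treatment period, so a CR first reached on the two drugs together satisfies the definition.

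At stake is the attribution of responses in the primary endpoint and three secondary ones. The duration endpoints inherit the problem, because Section 8.7.4 restricts them to patients who achieved the corresponding response. The error can only raise the azacitidine rate. In the planned comparison with Study 5F9005 that would make magrolimab's contribution look smaller than it is.

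**Working it through.** **Step 1. Does any other rule close the window at an add-on?**

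- *Wording elsewhere.* Where the protocol wants the first of two dates it says so, as in TTNT (Section 8.1.2) and the data-collection end (Section 8.2.1). The response window has no such words.
- *Eligibility.* Inclusion Criterion 4 and Exclusion Criterion 10 both look at how azacitidine was started. Exclusion Criterion 3 removes participants in interventional trials, not patients given an added agent in routine care.
- *Data collection.* Table 8-2 has no add-on scenario. Under Scenario A, a patient who stays on azacitidine is followed to 01 January 2021, so responses after an add-on are captured.
- *Adjudication.* Section 8.9 has the assessor examine responses that meet the protocol definitions. It does not ask which treatment produced them.
- *Terms.* The response window refers to the next MDS treatment and TTNT to the next anti-leukemic treatment. Neither says whether an agent added to continuing azacitidine qualifies, and the Table 8-4 label suggests therapy that follows azacitidine.

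Result: an added agent can end TTNT on its start date while a CR found later is still counted as a monotherapy CR.

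**Step 2. The protocol's own precision figures.** Table 8-5 uses exact Clopper-Pearson limits. For x responders among n, the lower limit is the 2.5% quantile of Beta(x, n − x + 1) and the upper limit is the 97.5% quantile of Beta(x + 1, n − x). With x = 40 and n = 400 this gives 7.2% to 13.4%, as printed. All 25 cells reproduce to 0.1 point with responders rounded half up. The half-width at 10% and 400 patients is (13.4 − 7.2)/2 = 3.1 points.

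**Step 3. Effect per response.** Each add-on CR wrongly counted adds 1/400 = 0.25 points. If 40 of 400 CRs were observed and some were add-on CRs, removing them gives:

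| Add-on CRs removed | CR rate | Exact 95% CI |
|---|---|---|
| 0 | 10.0% | 7.2% to 13.4% |
| 4 | 9.0% | 6.4% to 12.2% |
| 8 | 8.0% | 5.5% to 11.1% |
| 12 | 7.0% | 4.7% to 10.0% |

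The shift exceeds the 3.1-point half-width only from 13 add-on CRs upward (3.1/0.25 = 12.4).

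**Step 4. Illustrative range.** The protocol gives neither the share of patients with an added agent (s) nor their rate of first CR afterwards (q). Both are assumed here. Inflation in points = 100 × s × q.

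| Assumed s | q = 10% | q = 20% | q = 40% |
|---|---|---|---|
| 2% | 0.2 | 0.4 | 0.8 |
| 5% | 0.5 | 1.0 | 2.0 |
| 10% | 1.0 | 2.0 | 4.0 |

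Only the last cell exceeds 3.1 points.

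**The case against.** The best defence is that the second limb was meant only to carry the window past the last azacitidine dose until the next line begins, and that an added drug, if it is a TTNT event, is also the next MDS treatment that closes the window. That reading fits the monotherapy objective and may be what was intended. The text does not say it, however, and it works only if an add-on counts as a next treatment, which is left undefined.

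A second defence is that added agents can be identified and handled in the statistical analysis plan, which is not shown. The first half stands: the defect lies in the counting rule, not in lost data. But the protocol itself fixes the window for four endpoints, so an analysis that cut responses at an add-on would depart from the literal definition.

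Third, the bias runs against magrolimab, and Section 8.10 discloses an opposing one: missing marrow results lower the CR rate. Both are true. Neither makes a combination response a monotherapy response.

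Two stronger readings are tempting but not supported:

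- A reader might infer that responses after azacitidine is *resumed* following another therapy are also counted. Table 8-2 generally ends collection 30 days after discontinuation; beyond that it lists only survival and next treatment, plus progression date in Scenario C. Response is not listed.
- A reader might infer from the Table 8-4 label that later MDS treatment is recorded only once azacitidine has stopped. The row is marked at the on-treatment visits too, and concomitant medications and transplant have their own rows at those visits.

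**Conclusion.** The point holds for an anti-leukemic agent added to continuing azacitidine. On the literal text, a first response after that addition counts for CR, rw-CR, ORR and rw-ORR, and nothing else in the protocol prevents it.

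The size cannot be derived from the protocol. What is firm is 0.25 points per misattributed CR at 400 patients, always upward. The range of 0.2 to 4.0 points rests wholly on assumed rates and on every such CR being a first response after the add-on. The lower end is quite possible: the primary CR needs a marrow biopsy, and Section 8.10 says biopsies are not routine apart from diagnosis and suspected progression.

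A reader might infer that the primary estimate is materially inflated and that the study cannot proceed without a change. The protocol does not support that. This is an inexpensive improvement to the primary endpoint definition.

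**What to change.** In Sections 8.1.1 and 8.1.2, define the window as starting on the index date and closing just before the next anti-leukemic MDS treatment, including transplant, whether that treatment is added to azacitidine or replaces it. Make the closing event and its date the same as for TTNT, and use one term for both.

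State that the concurrent therapies allowed under Inclusion Criterion 6, and agents used for symptomatic support, do not close the window. Without this, permitted supportive care could be mistaken for a next treatment.

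Relabel the Table 8-4 row to cover MDS treatment started during or after azacitidine, which matches the visits already marked.

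The cost is a sentence in the endpoint definitions and one row label. The treatment data are already to be abstracted. The downside is that a few responses are no longer counted.
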